## 1 Statistical Analysis Plan

### 1.1 Study Overview

#### Background/Introduction:

Ventilator-induced lung injury (VILI) is a known cause of significant morbidity and mortality in patients with acute respiratory failure. Lung injury caused by large tidal volumes, high pressures, repetitive airway collapse, and large changes in trans-pulmonary pressure during a breath are all known to cause VILI. It has also been noted that similar lung damage can be caused by large, patient generated, uncontrolled tidal volumes and driving pressures – termed ‘self-induced lung injury’ (SILI). Patient-generated large tidal volumes may be disease induced (e.g. neurologic injury) or driven by other factors (metabolic derangements, anxiety). Interactions of patient efforts with assisted/supported models of mechanical ventilation may worsen this.

Pressure-support ventilation (PSV) is a common mechanical ventilation mode, often used in patients with active inspiratory efforts in order to reduce patient inspiratory work and improve comfort. PSV effectively allows spontaneously breathing patients to determine their breath flow-rate and breath duration, eliminating flow and cycle dyssynchrony.

### 1.1.1 Study Aims

1. Determine the internal consistency of four methods of measuring airway plateau pressure during pressure-support ventilation, utilizing:
  - a. The static respiratory driving pressure from ventilator in pressure support during inspiratory hold (Maneuver A; considered the gold-standard measurement)
  - b. The lung driving pressure in pressure support during first 0.1 seconds of inhalation (Maneuver B)
  - c. The occlusion pressure in pressure support (Maneuver C)
  - d. The static respiratory system driving pressure in volume control (Maneuver D)
2. The pairwise consistency of measures (AB, AC, AD, BC, BD, CD)

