ASOP is a prospective cohort study comparing three methods for assessing risk of self-induced lung injury in patients with acute respiratory failure being managed with pressure-support ventilation.

Specific Aim: We will describe the relationship between three different assessment methods for risk of self-induced lung injury and compare them to a gold standard measurement. The “gold standard” for SILI risk will be a direct assessment of transpulmonary Pplat and DP using an esophageal balloon tipped catheter to measure esophageal pressure (Pes) as a surrogate for pleural pressure. We will compare these to three assessment techniques using only the conventional airway pressure monitor: a plateau pressure and DP calculation in pressure support ventilation, an airway occlusion test in pressure support ventilation, and a plateau pressure and

DP calculation in volume-control ventilation in each patient. Our central hypothesis is that these three techniques will give similar results to “gold standard”.

4. Study Population

Inclusion Criteria:

- Adult patients (≥ 18) with acute respiratory failure receiving invasive mechanical ventilation
- Managed in pressure-support mode of ventilation

Exclusion Criteria:

- Actively undergoing a spontaneously awakening trial or SAT
- Patient or surrogate is unable to provide informed consent
- Currently pregnant
- Currently incarcerated
- Acute exacerbation of an obstructive lung disease
- Known esophageal varices or any other condition for which the attending physician deems an orogastric catheter to be unsafe
- Esophageal, gastric or duodenal surgical procedures within the last 6 months

5. Screening and Recruitment

Study staff will identify potentially eligible patients during the study period using medical records and lists maintained for clinical operations. If a potentially eligible patient is identified, their clinical team will be contacted to ensure that the patient is appropriate for inclusion in the study. If deemed appropriate for participation by the clinical team, the LAR will be approached for consent.

6. Process of obtaining informed consent

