- Dynamic change in airway pressure (“occlusion pressure”) and transpulmonary pressure during an airway occlusion maneuver during a pressure support breath
- Respiratory effort as measured by the ventilator p(0.1).
- Change in tidal volume with a decrease in set pressure-support
- Change in airway and transpulmonary plateau pressure with decreased pressure support
- Change in airway and transpulmonary driving pressure with decreased pressure support

Data collected from the EHR after study specific measurements will include

- Total duration of mechanical ventilation in days
- Total duration of intensive care length of stay in days
- Total duration of hospital length in stay in days
- Survival to discharge

No data will be collected after the patient is discharged from the hospital.

8. Randomization

This is a cohort study and there will be no randomization of patients to a treatment or control. Due to possible bias based of order of methods assessed, we will randomize the order that each patient is tested, including the gold standard (A) and the three methods of interest (B, C and D). Randomization schema will be a simple randomization of the methods for each patient, where each patient will be assessed on all 4 methods. A list of method order will be created prior to study start with order consisting of (e.g. ABCD, BCDA, CDAB, etc).

9. ASOP procedures.

ASOP is a prospective cohort study comparing three methods for assessing risk of self-induced lung injury to a gold-standard measurement in patients with acute respiratory failure being managed with pressure-support ventilation.

The study will compare the following four methods for assessing risk for SILI during PSV:

1. The transpulmonary plateau and driving pressure during a volume control. This will be considered the gold standard measurement of both plateau and driving pressure.
2. The airway plateau and driving pressure during a volume control breath.
3. The airway plateau and driving pressure during a pressure support breath
 - a. This variable will be measured in two ways. Once using an inspiratory hold on the Servo ventilator, and once using a Resironics NM3 device with VentAssist SoftWare.
4. The dynamic change in airway pressure and transpulmonary pressure during an end expiratory occlusion maneuver during a pressure support breath.

After enrollment, all baseline ventilator settings will be recorded (including PEEP, pressure support, tidal volume, and FiO2).

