- ix) Calculate transpulmonary driving pressure from ventilator and esophageal balloon ([a.4-a.5]-[a.1-a.3]) for each recorded breath
- x) Record P(0.1) from ventilator for 5 breaths (a.10)

b) Measure dynamic respiratory system driving pressure (DPrs-dyn) and transpulmonary driving pressure (DPtp-dyn)

- i) Record PEEP from ventilator (b.1)
- ii) Record PEEP from NM3 monitor (b.2)
- iii) Record end-expiratory esophageal pressure during a breath (b.3)
- iv) Record maximum airway pressure (b.4)
- v) Record maximum inspiratory esophageal pressure (b.5)
- vi) Record Airway plateau pressure from NM3 monitor (b.6)
- vii) Repeat for 5 total measurements of each variable
- viii) Calculate dynamic driving pressure across the respiratory system (DPrs-dyn) (b.7 = b.4-b.1)
- ix) Calculate dynamic transpulmonary driving pressure (DPtp-dyn) (b.8 = ([b.4-b.5]-[b.1-b.3]))
- x) Calculate the dynamic driving pressure across the respiratory system from the NM3 monitor DPrs-Dyn-NM3 (b.6-b.2)

c) Measure airway occlusion test (AOC)

- i) Measure PEEP (c.1)
- ii) Measure end expiratory esophageal pressure (c.2)
- iii) Perform expiratory hold
 - (1) Expiratory hold should be held for entirety of respiratory effort until airway pressure returns to baseline
 - (a) Measure maximum negative deflection of airway pressure (c.3)
 - (b) Measure maximum negative deflection of esophageal pressure (c.4)
- iv) Repeat 5 total measurements of each variable
- v) Calculate airway occlusion pressure (AOC = c.1-c.3) for each breath

d) Measure static respiratory system (DPrs-vc) and transpulmonary driving pressure (DPtp-vc) in volume control breath

- i) Change ventilator mode to SIMV (PSV+VC), with IMV breaths set in Volume control.
 - (1) Set PSV settings identical to baseline settings recorded in section 2.
 - (2) For VC breaths, volume set to average tidal volume calculated in section 2. subsection D.
 - (3) Set rate of IMV breaths to 1/min
 - (4) Set flow rate for VC breaths to minimum
- ii) Measure PEEP (d.1)
- iii) Measure end-expiratory esophageal pressure (d.2)
- iv) Measure airway plateau (d.3) during inspiratory hold
- v) Measure end-inspiratory esophageal pressure (d.4) during inspiratory hold
- vi) Repeat for 5 total measurements of each variable
- vii) Calculate respiratory system driving pressure (DPrs-vc = d.2-d.1)
- viii) Calculate transpulmonary plateau pressure (d.6 = d.2-d.4)

- ix) Calculate driving pressure across the lung ($DP_{tp-vc} = d.6 - (d.1-d.3)$)

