- e) Measure change in airway plateau pressure and patient effort with decrease in Pressure-support.
 - i) Ventilator will be returned to baseline settings
 - ii) The set pressure support will be decreased by 5 cm of H₂O (to a minimum of 5 cm of H₂O)
 - iii) The new tidal volume will be recorded (e.1)
 - iv) Measure PEEP (e.2)
 - v) Measure end-expiratory esophageal pressure (e.3)
 - vi) Perform and inspiratory hold in pressure-support
 - (1) Measure airway plateau pressure (e.4)
 - (2) Measure end-inspiratory esophageal pressure (e.5)
 - vii) Measure a P(0.1) (e.6)
 - viii) Repeat for 5 total measurements of each variable
- ix) Calculate new static respiratory system driving pressure (DP_{rs-new}) (e.7=e.4-e.2)
- x) Calculate new transpulmonary driving pressure (DP_{l-new}) (e.8=[e.4-e.5]-[e.2-e.3])
- f) Return all ventilator settings to baseline.

The order of performing these measurements will be randomized to minimize bias of the order of measurements.

All study specific measurements and maneuvers will be completed in one day. After completion of study measurements and maneuvers, the orogastric balloon will be removed.

A patient's EHR will be monitored until hospital discharge to collect previously mentioned study specific endpoints as described above.

Overall, we plan to enroll 25 patients.

10. Statistical design, analyses, sample size, and power

Statistical Design and Analysis Plan

Patient and clinical characteristics will be described overall using frequency and percent for categorical characteristics, and mean, standard deviation, median, and quartiles for continuous variables. Agreement statistics such as the intraclass correlation coefficient (ICC), Bland-Altman plots, and Cohen's kappa, will be used to assess agreement of measures between the gold-standard and the three methods of interest. A mixed-effects regression model will be used to determine the difference between each method and the gold-standard taking into account the randomization order with results presented as the least squares mean (LSM) difference with 95% confidence interval (CI). All analyses will be performed using SAS 9.4 (Cary, NC) and a p-value <0.05 will be considered statistically significant.

Sample Size and Power

This is a descriptive study. The 25-person sample size reflects the pragmatics of recruitment with available study staff and should provide adequate power to evaluate similarities given that each patient acts as his/her own control.

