## 1.3 Outcomes, Exposures, and Additional Variables of Interest

### 1.3.1 Maneuver Variables

Maneuver	Variable(s)	Description	Specifications

A	dprs_servo[1-5]	Static Respiratory System Driving Pressure from Ventilator	Calculated within REDCap as: pplat_servo_a[1-5] - peep_vent_a[1-5]
B	p0_1_[1-5]	P 0.1 from Servo	Entered directly into REDCap
C	paw_max_b[1-5]	Max Airway Pressure	Entered directly into REDCap
	peep_vent_b[1-5]	PEEP from Ventilator	Entered directly into REDCap
	aop_[1-5]	Airway Occlusion Pressure	Calculated within REDCap as: peep_vent_c[1-5] - max_neg_paw[1-5]
	pred_delta_pl_[1-5]	Predicted $\Delta P_L$	Calculated as: paw_max_b[1-5] - peep_vent_b[1-5] + (2/3)*aop_[1-5]
D	dprs_stat_vc_d[1-5]	Static Respiratory System Driving Pressure	Calculated within REDCap as: pplat_aw_d[1-5] - peep_vent_d[1-5]

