### 1.4.3 Analyses Plan for Aim 2

For each pair of maneuvers, the consistency of the measures between the two methods will be quantified using the interclass correlation coefficient  $\rho_{inter}$ .

$\rho_{inter}$  gives the correlation between any two measurements from the same patients from different methods.

Similarly to Aim 1, the  $\rho_{inter}$  is defined as

$$\rho_{inter} = \frac{\sigma_\alpha^2}{\sigma_\alpha^2 + \sigma_\gamma^2 + \sigma_\epsilon^2}$$

95% confidence intervals for each of the variances, as well as the ICC, will be calculated using the empirical 2.5th and 97.5th percentiles of 10,000 parametric bootstrap replications.

For each maneuver, the within-subject mean values will be calculated. For each pair of maneuvers (A and B, A and C, etc) the subject-level mean values will be plotted.

Summaries of the subject-level mean and standard deviations will be reported using mean with standard deviation, median with first and third quartiles, and range, stratified by maneuver.

Technical details:

The values for  $\sigma_\alpha^2, \sigma_\gamma^2, \sigma_\epsilon^2$  are estimated from the linear mixed effects-model

$$Y_{ijk} = \mu + \alpha_i + \beta_j + \gamma_{ij} + \epsilon_{ijk}$$

Where  $Y_{ijk}$  is the  $k$ th measurement coming from the  $i$ th patient using method  $j$ .

Here,  $i$  indexes the 15 patients,  $j$  indexes the either the first or second of the two methods (A or B, A or C, etc), and  $k$  indexes the breath number for patient  $i$  on method  $j$ . Because some measurements were discarded, each patient on each method has up to, but sometimes less than, 5 repetitions.

The various terms represent:

- $\mu$  = the overall mean value for method 1
- $\alpha_i$  = the subject-specific deviation from the overall mean for method 1
- $\mu + \alpha_i$  = the subject-specific mean for method 1
- $\beta_j$  = the deviation in the overall mean for method 2 from method 1
- $\mu + \beta_j$  = the overall mean for method 2
- $\gamma_{ij}$  = the subject-specific interaction term for method 2 (relative to the subject-specific deviation for method 1)
- $\alpha_i + \gamma_{ij}$  = the subject-specific deviation from the overall mean for method 2

We assume that

$$\alpha_i \sim N(0, \sigma_\alpha^2), \quad \gamma_{ij} \sim N(0, \sigma_\alpha^2), \quad \epsilon_{ijk} \sim N(0, \sigma_\epsilon^2)$$

With  $\alpha_i$ ,  $\gamma_{ij}$ , and  $\epsilon_{ijk}$  each iid and mutually independent of each other.

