#### 1.4.4 Bland-Altman Plot

A Bland-Altman (Tukey mean-difference) plot will be created for maneuvers A and D.

This plot will show the difference between measurements on the y-axis, and the average of measurements on the x-axis. 95% limits of agreement are calculated for the difference between measurements (y-axis) values by calculating the usual 95% confidence interval for the mean of the differences (that is, roughly, [mean of differences]  $\pm$  1.96 \* [standard deviation of the differences]).

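### The SAP drops the protocol's esophageal reference without explanation, so none of its analyses tests the protocol's hypothesis of agreement with that reference

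*SAP*

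**What the plan says.** **Protocol.** Section 3 sets the reference as "a direct assessment of transpulmonary Pplat and DP using an esophageal balloon tipped catheter", and section 9 fixes the ventilator mode: "The transpulmonary plateau and driving pressure during a volume control. This will be considered the gold standard measurement of both plateau and driving pressure". Airway pressures in volume control, airway pressures from a pressure-support hold, and the occlusion test are the three methods to be judged against it. Section 10 says that ICC, Bland-Altman plots and Cohen's kappa "will be used to assess agreement of measures between the gold-standard and the three methods of interest". It adds a mixed model giving each method's least-squares mean difference from the reference, with a 95% CI and allowance for the randomized order.

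**SAP.** Section 1.1.1 recasts the aim as consistency among four ways of measuring airway plateau pressure and names as its standard "The static respiratory driving pressure from ventilator in pressure support during inspiratory hold (Maneuver A; considered the gold-standard measurement". In section 1.3.1 Maneuver A is the "Static Respiratory System Driving Pressure from Ventilator", that is, airway plateau minus PEEP. Section 1.4.2 plans an ICC within each maneuver. Section 1.4.3 plans an interclass correlation (rho_inter) for the six pairs among A to D. In section 1.4.4 the Bland-Altman "plot will be created for maneuvers A and D".

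**The concern.** The quantity the SAP calls the gold standard is method 3 in the protocol's list, a technique under evaluation. The actual reference, and the esophageal readings needed to compute it, do not appear in the SAP's variables or analyses. The SAP does not say that the reference was changed, when or why, or whether protocol section 10 still applies.

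Two things are at stake. The study could be analysed exactly to its SAP and never address its central hypothesis, although patients have a catheter placed to obtain the readings that would address it. And a reader who sees Maneuver A labelled the gold standard could take good agreement between A and D as agreement with transpulmonary pressure.

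Timing adds weight. The SAP cites a data version dated February 22, 2024, counts 15 enrolled patients and notes that some measurements were discarded. It was therefore worded with data in hand, when a change of reference most needs a stated reason.

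**Working it through.** **1. Trace the reference through the SAP.**

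| SAP element | Content | Includes the protocol reference |
|---|---|---|
| Variables (1.3.1) | dprs_servo, p0_1, paw_max_b, peep_vent_b, aop, pred_delta_pl, dprs_stat_vc_d | 0 of 7 |
| Pairs (1.1.1, 1.4.3) | AB, AC, AD, BC, BD, CD | 0 of 6 |
| Bland-Altman plots (1.4.4) | A against D | 0 of 1 |

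The predicted transpulmonary pressure in Maneuver C is maximum airway pressure minus PEEP plus two thirds of the occlusion pressure. It has no esophageal term.

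**2. What separates airway from transpulmonary driving pressure.** Protocol step 5d labels its readings d.1 PEEP, d.2 end-expiratory esophageal pressure, d.3 airway plateau and d.4 end-inspiratory esophageal pressure. Then:

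- SAP Maneuver D = d.3 - d.1
- Reference DPtp-vc = (d.3 - d.4) - (d.1 - d.2)
- Difference = d.4 - d.2, the change in esophageal pressure

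No SAP variable contains d.2 or d.4, so no SAP result can bear on this difference.

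**3. Scale (assumed values; the documents give none).** For a passive breath, gap = airway DP x (1 - lung share of elastance).

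- Airway DP 12: 12 x 0.5 = 6.0 and 12 x 0.1 = 1.2 cmH2O. Relative to the reference, (1 - share)/share = 0.5/0.5 = 100% and 0.1/0.9 = 11%.
- Airway DP 8 to 16: from 8 x 0.1 = 0.8 to 16 x 0.5 = 8.0 cmH2O.

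Any difference between pressure-support and volume-control breaths comes on top and is not estimated.

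**4. Agreement between A and D says nothing about the reference.** Simulation with assumed airway DP of mean 12 and SD 3, measurement SD 1, and an esophageal change of mean/SD from 1/0.5 to 5/3 cmH2O:

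| Comparison | Bias | Limits of agreement | Correlation |
|---|---|---|---|
| A vs D, all settings | about 0 | about ±2.8 | 0.90 |
| A vs reference, change 1/0.5 | 1.0 | -2.0 to 3.9 | 0.89 |
| A vs reference, change 5/3 | 5.0 | -1.5 to 11.5 | 0.65 |

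**5. Adding the reference to the rho_inter analysis would not be enough.** In SAP 1.4.3 the fixed term beta_j, "the deviation in the overall mean for method 2 from method 1", is absent from the formula for rho_inter. With assumed SDs of 3 (patient), 1 (interaction) and 1 (breath), rho_inter = 9/(9 + 1 + 1) = 0.82 whatever the offset. Simulating 15 patients, two methods and five breaths with offsets of 0, 1.2, 4 and 6 cmH2O gave a median rho_inter of 0.81 to 0.82 each time, while mean bias was 0.0, 1.2, 4.0 and 6.0. (The interaction was given its own variance, as the formula implies; the distribution line in 1.4.3 prints the patient variance for it.)

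**6. Precision with 15 patients.** Half-width of the 95% CI for a bias, one difference per patient = t(14, 0.975) x SD/√15 = 2.145 x SD/3.873:

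- SD 2: 1.11 cmH2O
- SD 3: 1.66 cmH2O
- SD 4: 2.22 cmH2O

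A true bias equal to the half-width is detected only about half the time (power 51%). For 80% power the bias must be about 1.6 (SD 2) to 3.1 (SD 4) cmH2O. At 1.2 cmH2O power is 58% to 19%.

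**7. Can the reference be computed from the protocol's formulas?** Step 5d has index slips. It writes "Calculate transpulmonary plateau pressure (d.6 = d.2-d.4" and DPrs-vc = d.2 - d.1, although d.2 is an esophageal reading. With assumed d.1 = 5, d.2 = 8, d.3 = 17, d.4 = 11:

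| Quantity | As written | By the labels |
|---|---|---|
| DPrs-vc | 8 - 5 = 3 | 17 - 5 = 12 |
| Transpulmonary plateau | 8 - 11 = -3 | 17 - 11 = 6 |
| DPtp-vc | -3 - (5 - 17) = 9 | 6 - (5 - 8) = 9 |

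The two slips cancel in DPtp-vc, so the reference driving pressure is unaffected. The reference plateau pressure is not.

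**The case against.** **A SAP may narrow a protocol's aims, and its analyses do serve its own.** True, but it must say so. The text available gives no reason and keeps the gold-standard label. Front matter is missing from the copy reviewed, so the absence of a reason is asserted only for the numbered SAP sections. The mismatch itself does not depend on it.

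**Protocol section 10 has not been withdrawn.** This stands as a limit: the conclusion concerns an analysis done to the SAP. But the SAP supplies neither a reference variable nor an order variable with which to carry out section 10.

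**The protocol's own lettering is inconsistent.** This stands, and it may explain the slip, though that is inference. Section 8 calls the gold standard A, whereas step 5a is the pressure-support hold and the reference comes from step 5d. Read together, these reproduce the SAP's label. Both documents need correcting.

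**The cmH2O figures are assumptions.** This stands. The elastance formula presumes a passive breath; with persisting effort during the hold, the esophageal change could be smaller or negative. The figures show scale only, and the counts and the identity carry the argument without them.

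**The step 5d slips do not reach the SAP.** Correct for volume-control airway driving pressure, which SAP 1.3.1 computes properly, and for DPtp-vc. They matter only once transpulmonary plateau pressure is restored.

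**Conclusion.** The concern holds with high confidence and must be fixed. The documents name different references, and the SAP's is one of the methods the protocol set out to evaluate. The protocol's reference is missing from every variable, pair and plot in the SAP, so following the SAP leaves the central hypothesis untested. That conclusion rests on the text and an algebraic identity alone.

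On the assumed ranges, most of the possible gap between airway and transpulmonary driving pressure would be detectable with 15 patients. Gaps near the lower end, about 1 cmH2O, might well be missed.

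**What to change.** 1. Reconcile protocol step 5d. By its own labels, DPrs-vc is d.3 - d.1 and transpulmonary plateau is d.3 - d.4.
2. Add DPtp-vc to SAP 1.3.1 as the driving-pressure reference. Compare it with pressure-support-hold driving pressure (ventilator a.7 and NM3 a.8), volume-control airway driving pressure and the occlusion-based predicted pressure. State why that prediction stands in for the protocol's occlusion pressure. Compare transpulmonary plateau (d.3 - d.4) with airway plateau (a.4, a.6, d.3).
3. For each comparison report bias with limits of agreement and the order-adjusted least-squares mean difference with its 95% CI. Do not rely on rho_inter alone. Add maneuver order as a variable. The reference and volume-control airway driving pressure come from the same maneuver, so order drops out of that pair. Either include the protocol's ICC and kappa against the reference or say why they are dropped.
4. Keep the six existing pairs as secondary, remove the gold-standard label from Maneuver A, and use one set of maneuver letters in both documents, including protocol section 8.
5. If usable esophageal data are lacking, or the change of reference was deliberate, say so with the date and reason, restate the aim as consistency among airway measures, and report that the protocol's hypothesis was not tested.

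The cost is an SAP amendment, seven added comparisons (four for driving pressure, three for plateau pressure) and a merged order variable. No new patients or procedures are needed if the step 5d readings were recorded. Their completeness is not shown: 25 patients were planned, the SAP has 15, and some measurements were discarded.

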## 1.4 Statistical Analysis Plan

### 1.4.1 Demographic and Clinical Characteristics (“Table 1”)

The variables listed in Section 3.2 will be summarized for the cohort using mean with standard deviation, median with 25th and 75th percentiles (Q1, Q3), and min-max for continuous measures, and frequency with percentage for categorical measures.

### 1.4.2 Analyses Plan for Aim 1

The internal consistency of the static respiratory driving pressure (DPRS), that is to say the consistency of DPRS measures from the same patient, will be quantified for each maneuver (A, B, C, and D) separately using the intraclass correlation coefficient (ICC). The ICC measures the correlation of two observations coming from the same patient.

Specifically, the ICC is defined as

$$ICC = \frac{\sigma_{\alpha}^2}{\sigma_{\alpha}^2 + \sigma_{\epsilon}^2}$$

Where  $\sigma_{\alpha}^2$  is the variation in DPRS measurements between different patients, and  $\sigma_{\epsilon}^2$  gives the within-patient variation of DPRS measurements, with the sum  $\sigma_{\alpha}^2 + \sigma_{\epsilon}^2$  giving the total variation in DPRS values across all patients. Therefore, the ICC measures the proportion of total variation in the DPRS measurements that is due to variation between patients.

95% confidence intervals for each of the within-patient and between-patient variances, as well as the ICC, will be calculated using the empirical 2.5th and 97.5th percentiles of 10,000 parametric bootstrap replications.

General guidelines for interpretation of ICC values are as follows (Cicchetti, 1994):

- <0.40: poor consistency
- 0.40-0.59: fair consistency
- 0.60-0.74: good consistency
- 0.75-1.00: excellent consistency

Technical details:

The values of  $\sigma_{\alpha}^2$  and  $\sigma_{\epsilon}^2$  will be estimated from a linear mixed-effects model, with

$$Y_{ij} = \mu + \alpha_i + \epsilon_{ij}$$

With  $Y_{ij}$  being the  $j$ th DPRS measurement from the  $i$ th patient, with up to 5 measurement each from the 15 patients enrolled.

Here, the underlying mean DPRS value is  $\mu$  and the subject-specific deviation from the overall mean is given by  $\alpha_i$  for the  $i$ th patient, and the within-patient variation of measurements is given by  $\epsilon_{ij}$ .

We assume that

$$\alpha_i \sim N(0, \sigma_\alpha^2), \epsilon_{ij} \sim N(0, \sigma_\epsilon^2)$$

With  $\alpha_i$  and  $\epsilon_{ij}$  each iid and independent of each other.

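### Maneuver B is labelled a lung driving pressure but is raw P0.1, and ρ_inter is the between-method correlation only under equal variances and with γ on both methods

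*SAP*

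**What the plan says.** SAP 1.1.1 sets out four methods of measuring airway plateau pressure in pressure support. The second is "The lung driving pressure in pressure support during first 0.1 seconds of inhalation (Maneuver B"). SAP 1.3.1 gives the variable behind it: p0_1_[1-5], described as "P 0.1 from Servo" and entered directly. SAP 1.4.2 then treats all four maneuvers as one quantity, static respiratory driving pressure (DPRS): "consistency of DPRS measures from the same patient, will be quantified for each maneuver (A, B, C, and D) separately".

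The protocol handles P0.1 differently. Section 7 lists "Respiratory effort as measured by the ventilator p(0.1"). Section 9 announces "The study will compare the following four methods for assessing risk for SILI during PSV", and P0.1 is not in the list that follows. In step 5a it is a separate recording: "Record P(0.1) from ventilator for 5 breaths (a.10"). Step 5e is headed "Measure change in airway plateau pressure and patient effort with decrease in Pressure-support", which names plateau pressure and effort as two things; P0.1 is item e.6 there.

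For the pairs, SAP 1.4.3 says ρ_inter "gives the correlation between any two measurements from the same patients from different methods". It is defined as σα²/(σα² + σγ² + σε²). The model has a mean shift βj and one variance per random term, not indexed by method. The technical details describe γ as an interaction for method 2, relative to method 1.

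**The concern.** There are two linked problems.

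The first is what B is. Three of the six pairwise results (AB, BC, BD) involve it. Under the present wording they can be read as consistency between plateau or driving-pressure methods, when one side is an effort index.

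The second is what ρ_inter is. A coefficient built on shared variances falls when the two measures have different spread, even if they track each other closely. A low value then mixes scale with tracking. As a ratio of variances it also cannot go below zero, so it cannot show a negative association. If it is reported as the correlation, the reader is told something the model need not deliver.

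**Working it through.** **Label.** The variables in SAP 1.3.1, side by side:

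- A: plateau pressure minus PEEP, inspiratory hold in pressure support.
- B: P0.1 as read from the ventilator, with no plateau, PEEP or esophageal term.
- C: maximum airway pressure minus PEEP, plus 2/3 of the occlusion pressure (predicted ΔP_L).
- D: plateau pressure minus PEEP, volume control.

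No driving-pressure formula in the protocol uses P0.1. Protocol step 5b, which shares the letter B, is a different quantity: the dynamic respiratory-system and transpulmonary driving pressure. Going by variable names, its maximum airway pressure and PEEP enter the SAP under Maneuver C.

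**ρ_inter with γ on both methods**, as its denominator implies. Under the SAP's assumptions, the covariance of two breaths by different methods is σα², and each variance is σα² + σγ² + σε². The identity with the correlation is then exact.

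Now let the single-breath variances be V1 and V2, with a non-negative covariance.

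- The shared-variance fit targets Cov / [(V1 + V2)/2].
- The correlation is r = Cov / √(V1·V2).
- With k = SD1/SD2, ρ_inter = r × 2k/(1 + k²).

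The documents give no SDs, so k is an assumed range. The fitted column uses expected moments with 5 breaths per method, patient-level correlation 0.8 and breath SD 25% of patient SD. True r = 0.8/(1 + 0.25²) = 0.753.

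| k | 2k/(1+k²) | Loss | Fitted ρ_inter |
|---|---|---|---|
| 1 | 1 | 0% | 0.753 |
| 1.25 | 2.5/2.5625 = 0.976 | 2% | 0.735 |
| 2 | 4/5 = 0.80 | 20% | 0.602 |
| 3 | 6/10 = 0.60 | 40% | 0.452 |
| 4 | 8/17 = 0.47 | 53% | 0.354 |

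Simulation (4,000 datasets of 15 patients × 5 breaths, balanced moment estimates) gave these medians and 5th to 95th percentiles:

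- Shared variance: 0.75 (0.50–0.88) at 1:1, 0.60 (0.39–0.74) at 2:1, 0.35 (0.22–0.46) at 4:1.
- Method-specific variances: 0.76 (0.52–0.88) at all three.

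With a true correlation of −0.471, the shared-variance estimate was 0 in about 97% of datasets at 1:1, 2:1 and 4:1. The method-specific median was −0.49 to −0.48.

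**ρ_inter with γ on method 2 only**, as the term list describes. The two variances are then σα² + σε² and σα² + σγ² + σε², so the model's own correlation is σα²/√[(σα² + σε²)(σα² + σγ² + σε²)]. That is not the printed formula. For illustrative variances 1, 0.5 and 0.2, the printed formula gives 1/1.7 = 0.588 and the correlation is 1/√(1.2 × 1.7) = 0.700.

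Fitted to the scenario above (true 0.753), this form gives 0.683 at equal SDs, whichever method is listed second. At 2:1 it gives 0.67 or 0.33, depending only on which method is second.

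The assumptions line of SAP 1.4.3 also prints the variance of γ as σα². This is probably a misprint for σγ², the symbol used elsewhere in that section.

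**The case against.** **The label can be decoded.** The phrase itself mentions the first 0.1 seconds, and the variable table names P0.1. A careful SAP reader can work out what B is, and relabelling changes no number. That stands: it is a wording defect. But results will be reported under the wording of the aim.

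**The variable, not the label, may be wrong.** Because protocol step 5b is a dynamic driving pressure, a reader might infer that the wrong variable was pulled for B. The documents do not support that: the 0.1-second wording points to P0.1. Step 5a also names P0.1 in its heading beside the driving pressures. The sponsor should still confirm.

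**The model is not a B problem.** Correct. The shared variances and the γ conflict apply to all six pairs, and Maneuver C is also built differently from A and D. Equal SDs simply have least support where B is involved. Re-modelling only three pairs would leave the six results not comparable.

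**An ICC may rightly penalise scale.** As a consistency index, yes, and the aim speaks of consistency. The SAP's sentence is also exact under its stated assumptions. But the SAP presents the index as the correlation, and P0.1 is a different quantity from the other three.

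**Consequence is limited.** The planned plots of patient means and the summaries by maneuver would show a scale gap or a negative trend. The poor-to-excellent bands are stated only for Aim 1, and Bland-Altman covers only A and D. All of that stands.

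**Conclusion.** The label conflict is documented and needs no assumption: B is raw P0.1, so AB, BC and BD are associations between an effort index and driving-pressure measures.

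The model point is conditional. With γ on both methods, ρ_inter equals the correlation only at equal total variances and non-negative covariance. The shortfall runs from 0% at 1:1 to 53% at 4:1 over an assumed range. With γ on method 2 only, the printed formula is not the correlation even at equal SDs (0.68 against 0.75).

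A reader might infer that the B-pair results will be badly understated, or that a real negative association will be hidden. The documents support neither: they give no SDs and no expected sign, and at 1.25:1 the loss is trivial beside an interval of about 0.50 to 0.88. Nor is the Aim 1 ICC for B invalid; only its label is wrong. The study is descriptive and no decision rule uses these pairs. The change should be made, but no trial conclusion depends on it. The simulated figures assume balanced data, whereas the SAP notes that some measurements were discarded.

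**What to change.** 1. Confirm that P0.1 is the intended Maneuver B variable. If so, call it P0.1 (respiratory effort) in SAP 1.1.1 and 1.4.2, and reconcile the SAP and protocol lists of methods.
2. State in SAP 1.4.3 that γ applies to both methods, with its own variance σγ².
3. For all six pairs, and at least for AB, BC and BD, report the between-method correlation from a bivariate mixed model with method-specific patient and residual variances. Present the B pairs as association, not agreement.
4. Keep the shared-variance ρ_inter alongside for all six pairs, described as an index that also falls when scales differ, so that the pairs stay comparable.

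Cost: SAP wording and a re-coded model; no new data. The model has five variance-covariance parameters (two patient variances, their covariance, two residual variances) instead of three, with 15 patients. In the balanced simulation at equal SDs the spread was almost the same (0.52–0.88 against 0.50–0.88). However, that used moment estimates. Convergence of fitted bivariate models with unequal breath counts, and across the 10,000 bootstrap refits, was not tested. SAP 1.2.3 dates the data 22 February 2024, so record the change as made after that download.
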